**Table 14: Operating characteristics of the BOIN design**

	Dose Level					Number of Patients	% Early Stopping
	1	2	3	4	5		
Scenario 1							
True DLT Rate	0.25	0.41	0.45	0.49	0.53		
Selection %	67.6	16.9	6	1.4	0.2		7.9
% Pts Treated	43.5	34.3	17.6	3.9	0.7	18.4	
Scenario 2							
True DLT Rate	0.12	0.25	0.42	0.49	0.55		
Selection %	25.9	53.5	16.9	2.8	0.2		0.7
% Pts Treated	24.2	41.1	27.1	6.4	1.1	21.2	
Scenario 3							
True DLT Rate	0.04	0.12	0.25	0.43	0.63		
Selection %	1.8	23.8	60.5	13.5	0.4		0
% Pts Treated	8.4	25.7	41.8	20.6	3.4	22.1	
Scenario 4							
True DLT Rate	0.02	0.06	0.1	0.25	0.4		
Selection %	0.3	2.3	21.4	58.3	17.7		0
% Pts Treated	5.3	8.6	30.3	37.3	18.5	22.9	
Scenario 5							
True DLT Rate	0.02	0.05	0.08	0.11	0.25		
Selection %	0.5	0.9	7.3	22.1	69.2		0
% Pts Treated	5.2	7.5	20.6	30.4	36.4	21.6	

**Note:** "% Early Stopping"" refers to early stopping due to excessive DLT.

### 10.2.2. Sample Size for Safety Expansion

After the dose escalation is completed, select the MTD based on isotonic regression as specified ([Liu 2015](#)).

To better characterize and optimize RP2D, depending on the toxicity and PK/PD data, backfill (up to 6 additional subjects per dose) could start during the dose escalation given the dose has been deemed tolerable by the design, and could be performed at more than two doses.

After Dose Escalation has been completed, safety expansion up to 14 subjects per dose (including subjects treated at that dose level in the dose escalation phase) will be performed.

The doses for safety expansion are required to be no higher than the MTD and show sufficient PK/PD and anti-leukemic activities. The RP2D will be chosen based on an overall assessment of DLTs, safety profile, subject tolerance, biological activities and clinical efficacy signals collected at all different doses tested. The RP2D is required to be no higher than the MTD. A Bayesian toxicity monitoring rule will be used to ensure safety during safety expansion. At the RP2D, if 3 or more responses are observed, up to an additional 14 subjects may be enrolled to further evaluate its antitumor activities, safety and tolerability. Among the total of 28 subjects at the RP2D, if 9 or more responses are observed, the treatment is regarded as promising.

At the RP2D, the futility stopping rule (i.e., the safety expansion is subject to potential termination if 2 or fewer responses are observed among the first 14 subjects) yields the operating characteristics listed in [Table 15](#) based on simulation.

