**Table 15: Futility Stopping Rule**

Scenario	Response Rate	Early Stopping (%)	Claim Promising (%)	Average Sample Size
1	0.2	44.81	8.67	21.7
2	0.4	3.98	84.06	27.4
3	0.5	0.65	97.84	27.9

During safety expansion, we monitor toxicity using the Bayesian optimal phase 2 (BOP2) design ([Zhou, Lee, and Yuan 2017](#)). [Table 16](#) below provides the stopping boundaries of the BOP2 design.

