**Table 16: Optimized Stopping Boundaries**

No. of subjects treated	Stop if no. of toxicity >=
6	2
12	4
18	5
28	7

If the stopping boundaries are crossed, the subject accrual to that dose will be halted and the totality of safety data will be reviewed for potential termination of that dose.

Let  $p_{tox}$  denote the true toxicity rate, the above stopping rule is obtained by maximizing  $\Pr$  (claim that the treatment is safe |  $p_{tox} = 0.15$ ), while controlling  $\Pr$ (claim that the treatment is safe |  $p_{tox} = 0.25$ )  $\leq 0.3$ , based on the following Bayesian stopping rule: the treatment is deemed unacceptably toxic if

$$\Pr(p_{tox} \leq 0.25 | data) < \lambda \left( \frac{n}{N} \right)^{\alpha/3},$$

where,  $n$  is the interim sample size,  $N$  is the maximum sample size, and  $\lambda=0.55$  and  $\alpha=0.07$  are design parameters optimized, assuming a vague prior Beta(0.25, 0.75) for  $p_{tox}$  to make “go/no-go” decision. Note that the original publication of the design used the probability cutoff  $\lambda(n/N)^\alpha$ , here the attenuation factor 3 is added (i.e.,  $\alpha/3$ ) to obtain stricter interim stopping boundaries to enhance safety.

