**Below in [Table 17](#) are the operating characteristics of the design based on 10,000 simulations.**

**Table 17: Operating Characteristics**

Scenario	Toxicity Rate	Early Stopping (%)	Claim Acceptable (%)	Average Sample Size
1	0.33	84.03	7.99	11.3
2	0.25	62.85	27.97	15.7
3	0.15	27.64	69.63	22.4
4	0.05	3.38	96.61	27.3

**Note:** Since NC525 is a humanized monoclonal antibody, infusion reactions may occur. Furthermore, treatment of advanced myeloid neoplasms may cause differentiation syndrome and tumor lysis syndrome. Therefore, such events will be categorized as ECIs. Although these events may contribute to Dose Limiting Toxicities, they will be excluded when calculating the toxicity rate for evaluation of the stopping rule, except for Grade  $\geq 3$  differentiation syndrome that has not resolved within 7 days. All other events as defined in the DLT Table (Table 6) will be used as the criteria to evaluate the severe toxicity rate in the calculation of the stopping rule.

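### Table 17 and the 0.3 limit are computed for 28 fresh subjects at an unselected dose, but the expansion toxicity rule runs on selected doses and counts their escalation subjects

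*Combined protocol and SAP*

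**What the plan says.** Section 10.2.2 sets the expansion size: "safety expansion up to 14 subjects per dose (including subjects treated at that dose level in the dose escalation phase) will be performed". At the RP2D up to 14 more may follow, and the efficacy criterion is then applied "Among the total of 28 subjects at the RP2D". The escalation subjects are therefore part of the 14, and so of the 28.

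The toxicity rule is introduced with "During safety expansion, we monitor toxicity using the Bayesian optimal phase 2 (BOP2) design". Table 16 is indexed by the number of subjects treated at the dose, and its column "Stop if no. of toxicity >=" gives 2 of 6, 4 of 12, 5 of 18 and 7 of 28. The text below it says that the boundaries maximise the chance of a safe claim at a true rate of 0.15 while holding that chance to at most 0.3 at a true rate of 0.25, "assuming a vague prior Beta(0.25, 0.75) for" the toxicity rate. Table 17 is introduced with the words that below "are the operating characteristics of the design based on 10,000 simulations". At a rate of 0.25 it reports 62.85% early stopping, 27.97% claimed acceptable and an average sample size of 15.7.

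Neither table mentions carried-over subjects or dose selection. The plan also does not say whether a look at 6 or 12 that fell during escalation is applied to those subjects.

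**The concern.** The monitoring rule is used only in expansion, and a dose reaches expansion only after escalation under Table 1 and a finding that it is no higher than the MTD. Much of the protection that Table 17 reports comes from the look at 6 subjects. At a true rate of 0.25 that look supplies 46.6 of the 62.85 points of early stopping, about three quarters. Table 1 de-escalates at 2 DLTs in 6, the same count at which Table 16 stops. A dose that went through escalation with at most 1 in 6 has already cleared that look, so it cannot trigger again.

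At stake is the stated error control. A safety review relying on the 0.3 limit would take it as the property of the rule on the doses it monitors. The plan does not show that property for those doses.

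**Working it through.** **Inputs.** Looks and boundaries from Table 16; prior Beta(0.25, 0.75), λ = 0.55 and exponent α/3 with α = 0.07 from the text below it; escalation actions from Table 1; target 0.25, maximum 12 per dose, maximum 30 in total, and stopping at 9 evaluable subjects on a *stay* decision from section 10.2.1; MTD by isotonic regression from section 10.2.2.

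**Step 1: reproduce the plan.** The posterior rule gives boundaries 2/6, 4/12, 5/18 and 7/28, as printed. An exact binomial recursion over the four looks, starting from subject 1 with no selection, gives:

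| True rate | Early stop | Acceptable | Average N |
|---|---|---|---|
| 0.33 | 0.8403 | 0.0799 | 11.3 |
| 0.25 | 0.6285 | 0.2797 | 15.7 |
| 0.15 | 0.2764 | 0.6963 | 22.4 |
| 0.05 | 0.0338 | 0.9661 | 27.3 |

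All four rows agree with Table 17, which is therefore the fresh-dose calculation.

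**Step 2: the first look at a true rate of 0.25.**
- Chance of 0 in 6: 0.75^6 = 0.1780. Chance of 1 in 6: 6 × 0.25 × 0.75^5 = 0.3560.
- Chance of stopping at 6: 1 − 0.1780 − 0.3560 = 0.466. Share of early stopping: 0.466 / 0.6285 = 74%.
- Acceptable after 0/6 is 0.669 and after 1/6 is 0.451. Check: 0.1780 × 0.669 + 0.3560 × 0.451 = 0.280, the stated figure.
- Given at most 1 in 6: 0.2797 / 0.5339 = 0.52.

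**Step 3: exact chance of acceptable at 0.25 by entry state, remaining looks only.**

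| DLTs/subjects at entry | Table 1 action | Chance of acceptable |
|---|---|---|
| 0/3 | escalate | 0.473 |
| 1/3 | stay | 0.190 |
| 1/6 | escalate | 0.451 |
| 1/9 | escalate | 0.636 |
| 2/9 | stay | 0.389 |
| 3/9 | de-escalate | 0.137 |
| 2/12 | escalate | 0.596 |
| 3/12 | stay | 0.325 |

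Two of these worked through:
- From 3/12, passing the look at 18 needs at most 1 in the next 6, and passing at 28 needs a total of at most 6. This gives 0.1780 × P(at most 3 of 10) + 0.3560 × P(at most 2 of 10) = 0.1780 × 0.776 + 0.3560 × 0.526 = 0.325.
- From 2/9, the next 3 subjects add 0 or 1 event, each with probability 0.422; 2 or more stops at 12. This gives 0.422 × 0.596 + 0.422 × 0.325 = 0.389.

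The 2/9 state matters because section 10.2.1 ends escalation at 9 evaluable subjects on *stay*, and Table 1 says *stay* at 9 only for exactly 2 DLTs.

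**Step 4: average over entry states.** Escalation was simulated 12,000 times per Table 14 scenario (Table 1 actions, stopping at 9 on *stay*, plain isotonic selection of the dose nearest 0.25), and the selected dose's own data were carried into Table 16. Given that the 25% dose is the selected MTD, the chance of acceptable is:
- 0.33 to 0.44 if only looks not yet passed apply;
- 0.25 to 0.36 if the looks at 6 and 12 are also applied to escalation subjects.

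A separate run gave 0.33 to 0.43 and 0.24 to 0.35. The ranges used below span both runs. With accelerated titration confined to dose level 1, the simulator matches Table 14's MTD selection rates only to about 4 to 6 percentage points, so these averages are approximate. Step 3 does not depend on the simulator.

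**The case against.** **The arithmetic is correct, and the limit is stated given the true rate only.** This stands. A reader might infer that Table 17 is miscalculated, but every row reproduces. The fault is one of scope: the figure describes a dose that has not been through selection, and the rule is applied only to doses that have.

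**The MTD is not picked for a low DLT count.** This stands and limits the size. Isotonic regression picks the dose nearest 0.25. In the simulations the pooled observed DLT rate at a selected 25% dose was 0.205 to 0.249, and entry states such as 3/9 lower the chance of acceptable. A reader might infer that the true figure is generally 0.4 to 0.5. The documents do not support that. Values of 0.47 (0/3) or 0.52 (at most 1/6) belong to doses whose Table 1 result was escalate, such as a dose below the MTD or the top dose. Averages of 0.50 or more for the MTD appeared only under an added cap on the MTD estimate, which the plan does not contain and which fits Table 14 worse.

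**If all looks are applied to carried-over subjects, the inflation is small or absent.** This stands as a possibility, because 0.24 to 0.36 straddles 0.3. The plan does not say that this is what is done.

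**The excess is conditional on selection.** True: with no accelerated titration in Scenario 3, the joint chance that the 25% dose is selected and then called acceptable is 0.541 × 0.398 = 0.22. But the rule never runs on an unselected dose, so the conditional figure is the one relevant to expansion.

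**Crossing a boundary leads to a halt and review, and RP2D choice rests on all the data.** This stands and keeps the point moderate. It does not supply the missing operating characteristics.

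**Conclusion.** The point holds as a mismatch between the stated operating characteristics and the doses monitored. At a true rate of 0.25, against 27.97% stated and a limit of 0.3:
- about 0.33 to 0.44 for a dose selected as MTD, if only remaining looks apply (exactly 0.389 at 2/9 and 0.325 at 3/12);
- about 0.24 to 0.36 if the looks at 6 and 12 also apply to carried-over subjects.

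On the first reading the 0.3 limit is exceeded in all five Table 14 scenarios. On the second it may or may not hold. A reader might infer that the limit certainly fails; the documents do not settle that, because they do not say which looks apply.

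The figures assume that DLTs equal the monitored toxicity. The note under Table 17 excludes infusion reactions, tumor lysis syndrome and most differentiation syndrome from the stopping-rule rate. They also assume no backfill (section 10.2.2 allows up to 6 per dose), the five dose levels of Table 14 although six are now planned, plain isotonic selection, and accrual to 28 as in Table 17. The correction is worth making but does not make the monitoring unusable.

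**What to change.** 1. State in section 10.2.2 whether the Table 16 looks at 6 and 12 apply to escalation subjects carried into the count.
2. Replace Table 17 with a joint simulation of Table 1, MTD selection and Table 16, using the current six dose levels, any backfill, and the toxicity definition actually monitored. Alternatively, give rows by entry state, such as 0/3, 1/6, 2/9 and 3/12.
3. Restate the 0.3 limit as the figure that simulation delivers. If 0.3 must hold for doses in expansion, re-optimise λ and α under the joint simulation.

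The cost is a short simulation and a somewhat less favourable stated figure. No extra patients are needed.

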**Table 1: Dose escalation/de-escalation rule for the BOIN Design**

Escalation/De-escalation Rules														
Action**	Number of evaluable patients treated*													
	3	4	5	6	7	8	9	10	11	12	13	14	15	
Escalate if number of DLT $\leq$	0	0	0	1	1	1	1	1	2	2	2	2	2	2
Stay at current dose if number of DLT is equal to	1	1	1	NA	2	2	2	2	3	3	3	3	3, 4	3, 4
De-Escalate if the number of DLT $\geq$	2	2	2	2	3	3	3	3	4	4	4	5	5	5
Eliminate if number of DLT $\geq$	3	3	3	4	4	4	5	5	6	6	6	7	7	

Note. "# of DLT" is the number of subjects with at least 1 DLT. When none of the actions (i.e., escalate, de-escalate or eliminate) is triggered, stay at the current dose for treating the next cohort of subjects.

\*A subject is considered evaluable if they have received at least four doses of NC525 and completed the 56-day DLT observation period or discontinued earlier due to an adverse event.

\*\*If de-escalation rule is met at Dose Level 1, alternative dose levels or administration schedules may be considered pending safety review and emerging data.

In addition to the BOIN dose finding rules, decisions to escalate to the next dose will be based on all available PK, PD, efficacy, safety, and tolerability data for the prior cohort(s). Efficacy measures consist of MLFS, CR, CRh, CRi and hematological recovery. Since NC525 targets and effectively kills leukemic blasts and LSC, PD marker comprises clearance of blasts from the marrow and peripheral blood. Further PD marker such as expression of LAIR-1 on blast cells to correlate with response will be assessed.

Two dose levels will be expanded to determine an optimal Recommended Phase 2 Dose (RP2D) and administration schedule of NC525. After Dose Escalation has been completed, safety

expansion up to 14 subjects per dose (including subjects treated at that dose level in the dose escalation phase) will be performed.

The doses for safety expansion are required to be no higher than the MTD and show sufficient PK/PD and anti-leukemic activities. The RP2D will be chosen based on an overall assessment of DLTs, safety profile, subject tolerance, biological activities and clinical efficacy signals collected at all different doses tested. The RP2D is required to be no higher than the MTD. A Bayesian toxicity monitoring rule will be used to ensure safety during safety expansion. Refer to [Section 10.2.2](#) for details.

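### Table 15 gives error rates for one dose fixed in advance, but the RP2D is chosen from two expanded doses partly on the same responses; the 8.67% false-promising rate can reach about 12%, and at most about 15%, if both doses have a 20% response rate

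*Combined protocol and SAP*

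**What the plan says.** Section 3.2.1 (text after Table 1) sets up the choice between doses: "Two dose levels will be expanded to determine an optimal Recommended Phase 2 Dose (RP2D) and administration schedule of NC525". Section 10.2.2 gives the size of each expansion: "safety expansion up to 14 subjects per dose (including subjects treated at that dose level in the dose escalation phase) will be performed". Doses admitted to expansion must also "show sufficient PK/PD and anti-leukemic activities", with no threshold given.

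Under Section 10.2.2 the RP2D is chosen on an overall assessment of DLTs, safety, tolerance and "biological activities and clinical efficacy signals collected at all different doses tested". No weights are given, and the time of the choice is not fixed.

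The response rules follow in the same section. The extension rule is "At the RP2D, if 3 or more responses are observed, up to an additional 14 subjects may be enrolled", and its futility counterpart applies "if 2 or fewer responses are observed among the first 14 subjects". The final rule is "Among the total of 28 subjects at the RP2D, if 9 or more responses are observed, the treatment is regarded as promising". Table 15 is introduced as what the futility rule yields at the RP2D. Its first row (response rate, early stopping %, claim promising %, average sample size) reads "0.2 44.81 8.67 21.7".

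The multiplicity entry in Table 13 says only that cohorts are evaluated independently. It makes no adjustment for choosing between doses.

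**The concern.** The rules in Section 10.2.2 count 28 subjects at the RP2D, and the first 14 of them are among those whose responses helped make that dose the RP2D. A dose that happened to respond well in its first 14 is more likely to be chosen, and it takes that favourable count into the 3/14 and 9/28 rules. A calculation for a dose fixed in advance does not include this.

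Two stated properties are at stake. The chance of calling a 20% response rate promising would be higher than 8.67%. The chance of stopping early at that rate would be lower than 44.81%. The second matters at least as much, because futility stopping is what Table 15 is titled for.

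**Working it through.** **Inputs.** From Section 10.2.2: 14 subjects in stage 1, stop at 2 or fewer responses, 14 more subjects otherwise, promising at 9 or more of 28. From Section 3.2.1: two doses expanded. From Table 15: the response rates 0.2, 0.4 and 0.5. Assumed, because the plan does not say: the second dose's true response rate, the weight of response in the choice, and the number of subjects per dose at selection.

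**Step 1: reproduce Table 15 for one fixed dose.** With X1 and X2 independent Bin(14, p):
- Early stopping = P(X1 ≤ 2).
- Claim promising = Σ over x = 3 to 14 of P(X1 = x) × P(X2 ≥ 9 − x).
- Average N = 14 + 14 × (1 − early stopping).

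| p | Early stopping | Promising | Average N |
|---|---|---|---|
| 0.2 | 44.81% | 8.67% | 21.7 |
| 0.4 | 3.98% | 84.06% | 27.4 |
| 0.5 | 0.65% | 97.84% | 27.9 |

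Every entry matches Table 15, so the table contains no selection step.

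**Step 2: add selection, both doses truly at 20%, 14 subjects each, response alone decides.** The chosen dose's stage 1 count is the larger of two independent Bin(14, 0.2) counts, M, so P(M ≤ x) = P(X1 ≤ x)².

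| x | P(X1 = x) | P(M = x) | P(X2 ≥ 9 − x) | Fixed dose: product | Best of two: product |
|---|---|---|---|---|---|
| 3 | 0.2501 | 0.2867 | 0.0439 | 0.01097 | 0.01257 |
| 4 | 0.1720 | 0.2697 | 0.1298 | 0.02233 | 0.03502 |
| 5 | 0.0860 | 0.1570 | 0.3018 | 0.02595 | 0.04739 |
| 6 | 0.0322 | 0.0627 | 0.5519 | 0.01780 | 0.03461 |
| 7 | 0.0092 | 0.0183 | 0.8021 | 0.00739 | 0.01468 |
| 8 | 0.0020 | 0.0040 | 0.9560 | 0.00193 | 0.00385 |
| ≥ 9 | 0.0004 | 0.0008 | 1 | 0.00038 | 0.00076 |
| Sum | | | | 0.0867 | 0.1489 |

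- Promising: 14.9%.
- Early stopping: 0.4481² = 0.2007, or 20.1%.
- Average N at the RP2D: 14 + 14 × 0.7993 = 25.2.

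**Step 3: partial weight.** Suppose response decides with probability w, and otherwise the choice is independent of response. Then promising = (1 − w) × 8.67% + w × 14.89%, and early stopping = (1 − w) × 44.81% + w × 20.07%.

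| w | Promising | Early stopping |
|---|---|---|
| 0 | 8.7% | 44.8% |
| 0.25 | 10.2% | 38.6% |
| 0.5 | 11.8% | 32.4% |
| 0.75 | 13.3% | 26.3% |
| 1 | 14.9% | 20.1% |

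**Step 4: other selection rules, both doses at 20%.**
- One dose is the default and is replaced only if the other leads by at least 2, 3, 4 or 5 responses: 13.9%, 12.4%, 10.8%, 9.6% promising.
- The choice is made on responses alone in only the first 3, 6, 9 or 12 subjects per dose: about 11.4%, 12.8%, 13.7%, 14.4% (simulated).

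**Step 5: unequal doses.** One dose is at 20%, the other is lower, and response alone decides. With the other at 15%, 10% or 5%, promising is 9.5%, 8.6% or 8.7%. The inflation almost disappears.

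**The case against.** The strongest reply is that Table 15 contains no wrong number. It is introduced as applying at the RP2D, which can be read as conditional on that dose, and 8.67% is nowhere called a controlled type I error. Efficacy is a secondary endpoint (Sections 1.2.3 and 2.2.2), and Section 3.3 rules out formal comparisons between subjects. No escalation decision or toxicity stop uses the figure, and the extension after 3 responses is discretionary. Response is also only one of several selection criteria. On an ascending dose ladder, two equal 20% rates are one scenario and need not be the likely one.

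Most of this stands, and it limits both the size and the severity. It does not remove the point. The first 14 subjects are not independent of the choice of RP2D when their responses inform it, so a fixed-dose calculation does not describe the written procedure. With equal 20% rates, any positive weight on response raises the false-promising rate, and the plan names response as a criterion.

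A reader might infer that the true rate simply is 12-15%. The documents do not support that as fact. It needs two doses both at 20%, about 14 subjects each at selection, and response deciding at least half the time.

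**Conclusion.** The point holds in limited form. Table 15 describes a single pre-specified dose and omits the selection step in Sections 3.2.1 and 10.2.2. With both doses at 20% and about 14 subjects each at selection, the false-promising rate lies between 8.7% (no weight on response) and 14.9% (response alone), and is 11.8% at half weight. Futility stopping lies between 44.8% and 20.1%, and is 32.4% at half weight. With the other dose at 15% or below, the false-promising rate is about 8.6-9.5%. The activity screen for entry to expansion has no threshold and is not modelled. Severity is moderate.

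Three further inferences should not be drawn:
- **Joint power.** A reader might multiply Table 15's power by Table 17's acceptance rate. That treats Table 16 as an automatic stop and toxicity as independent of response. The plan says that crossing a boundary halts accrual and prompts a review for potential termination.
- **Bias in the pooled response rate.** At a true 20%, the mean observed rate among trials that continue to 28 is 24.6% under best-of-two selection. It is already 23.9% for one fixed dose, because only trials with 3 or more of 14 continue. Selection adds about 0.7 points.
- **A bar of 10/28.** This does not follow as a correction. For one dose at 40% it would cut the chance of a promising result from 84.1% to 73.6%.

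**What to change.** Re-simulate Table 15 under the written sequence: two doses to 14 subjects, the RP2D choice over a stated range of weights on response, then the second 14 at the RP2D. Include both equal and unequal true response rates, and state the number of subjects assumed per dose when the choice is made. Restate early stopping, claim promising and average sample size from that simulation. Alternatively, keep Table 15, state that it holds only for a dose specified in advance, and give the range under selection beside it.

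In either case, report the response rate in the second 14 RP2D subjects separately beside the pooled 28, since those subjects play no part in a choice made before they enrol.

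The cost is one re-simulation, revised text in Section 10.2.2 and a less favourable stated error rate. No patients are added.
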